3.1.1 Stage 1: Dose-Escalation Cohort

The dose-escalation stage is designed to evaluate the safety, tolerability, MTD, pharmacokinetics, and any anti-tumor activity of vemurafenib when administered in combination with cobimetinib.

Stage 1 will be conducted in previously untreated or treated patients with BRAF^{V600E}-positive metastatic melanoma (unresectable Stage IIIc and Stage IV, according to the American Joint Committee on Cancer [AJCC] classification) OR those who have discordant/mixed progression on treatment with vemurafenib monotherapy in a previous clinical trial or postmarketing setting immediately preceding enrollment in this trial. Patients in the former category who were previously treated must have had no prior exposure to any BRAF or MEK inhibitor therapy. Please see Sections 4.2 and 4.3 for a detailed description of the eligibility criteria. Patients who have FDG-PET avid disease will undergo FDG-PET imaging as a PD biomarker and potential early readout of anti-tumor activity.

a) Starting Doses and Overall Study Design

[figure not shown]
A 3+3 dose-escalation schema will be used. The starting dose of vemurafenib will be 720 mg bid for 28 consecutive days of each 28-day cycle of combination dosing, which is one dose level below the single-agent MTD of 960 mg bid established in the vemurafenib Phase Ia trial (PLX06-02) and which is utilized in the dose-modification scheme in the Phase II and Phase III trials of vemurafenib. This dose level was selected in an attempt to maintain RAS/RAF/ERK pathway suppression in non-progressing melanoma lesions. The effectiveness of this dose is supported by data from the Phase I through III clinical trials. In the Phase I trial, approximately 30% of patients have required dose reductions to 720 mg bid, while continuing to show a response to vemurafenib monotherapy.

The starting dose of cobimetinib will be 60 mg per day for 14 consecutive days of each 28-day cycle of combination dosing, which is two dose levels below the single-agent MTD of 100 mg per day administered on this schedule as established in the cobimetinib Phase Ia trial (Study MEK4592g). Dose escalation will proceed in increments, taking into account the safety and tolerability of the combination.

b) Dose Escalation

[figure not shown]
The dose-escalation schema and plan are detailed in [Figure 4](#), [Figure 5](#), and [Table 5](#).

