Cohort 1A (Figure 5) will test the safety and tolerability of vemurafenib at a dose of 720 mg bid in combination with cobimetinib at 60 mg/day on a 21/7 day schedule. Cohorts 1B and 1C may enroll patients only after the Cohort 1A dose combination is declared safe and tolerable. Cohort 1B will test the safety and tolerability of vemurafenib at a dose of 960 mg bid in combination with cobimetinib at 60 mg/day on a 21/7 day schedule, and Cohort 1C will test the safety and tolerability of vemurafenib at a dose of 720 mg bid and cobimetinib at 60 mg/day on a continuous schedule. After both Cohorts 1B and 1C are deemed to be acceptably safe and tolerable, Cohort 1D will open to evaluate the combination of vemurafenib at a dose of 960 mg bid and cobimetinib at 60 mg/day on a continuous schedule.

There will be no inpatient dose escalation during the DLT assessment window (Cycle 1, Days 1–28). After the DLT assessment window (Cycle 2 and beyond), patients without evidence of melanoma progression may receive cobimetinib at the highest cohort dose level for which there are at least 4 weeks of safety data demonstrating acceptable tolerability (i.e., no DLTs observed in a cohort of 3 evaluable patients or ≤ 1 DLT in a cohort of 6 evaluable patients). In some cases, this may allow the skipping of more than one dose level. For example, after Cohort 2A is determined to be safe and tolerable, patients in Cohort 2 may increase their daily dose of cobimetinib from 80 to 100 mg on a 14/14 schedule, and patients in Cohort 1 may increase their daily dose of cobimetinib from 60 to 100 mg on a 14/14 schedule. Patients that are beyond the Cycle 1 DLT assessment window are eligible for multiple, step-wise dose escalations (with agreement of the Sponsor's Medical Monitor) although dose escalations for an individual patient may not continue once that patient develops cobimetinib-related Grade ≥ 3 toxicity. Inpatient dose modification will be allowed in patients within a given cobimetinib administration schedule once the next higher dose level(s) is deemed to be acceptably safe and tolerable. Patients treated on a 14/14 schedule cannot transition to a 21/7 or a continuous daily schedule.

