In all such circumstances, the daily dose of vemurafenib may remain the same (at 720 or 960 mg bid) or increase from 720 to 960 mg bid, but only if the patient was tolerating 960 mg bid in a previous clinical study or postmarketing setting of vemurafenib monotherapy, immediately preceding enrollment in this trial.

All inpatient dose escalations must begin on Day 1 of the next treatment cycle.

Table 5 outlines the vemurafenib and cobimetinib dose and schedule combinations planned for Cohorts 1, 1A, 1B, 1C, 1D, 2, 2A, 3, 4, 5, and the cobimetinib monotherapy cohort. All cohorts except the cobimetinib monotherapy cohort will be open to patients who either have progressed on vemurafenib monotherapy or are previously untreated or treated (but without prior exposure to BRAF or MEK inhibitor therapy) for locally advanced/unresectable or metastatic melanoma.

Table 5 Roadmap for Planned Dose Escalation

Cohort (Patient number)	VEMURAFENIB/ Cobimetinib dose, schedule	Eligible patients	Comments
1 (n=3-6)	720 mg bid/60 mg qd 14/14	Vemurafenib progressors, PTPs, and PUPs	After (if) cohort 1 dose combination is deemed safe, cohorts 1A, 2 and 3 will open to new patients simultaneously
1A (n=3-6)*	720 mg bid/60 mg qd 21/7	Vemurafenib progressors, PTPs, and PUPs	
1B (n=3-6)*	960 mg bid/60 mg qd 21/7	Vemurafenib progressors, PTPs, and PUPs	Cohort 1B may open to new patients only after Cohort 1A dose combination is deemed safe and tolerable
1C (n=3-6)†	720 mg bid/60 mg qd 28/0	Vemurafenib progressors, PTPs, and PUPs	Cohort 1C may open to new patients only after Cohort 1A dose combination is deemed safe and tolerable
1D (n=3-6)†	960 mg bid/60 mg qd 28/0	Vemurafenib progressors, PTPs, and PUPs	Cohort 1D may open to new patients only after Cohort 1B and 1C dose combinations are deemed safe and tolerable
2 (n=3-6)	720 mg bid/80 mg qd 14/14	Vemurafenib progressors, PTPs, and PUPs	
2A (n=3-6)	720 mg bid/100 mg qd 14/14	Vemurafenib progressors, PTPs, and PUPs	Cohort 2A may open to new patients only after Cohort 2 dose combination is deemed safe and tolerable
3 (n=3-6)	960 mg bid/60 mg qd 14/14	Vemurafenib progressors, PTPs, and PUPs	
4 (n=3-6)	960 mg bid/80 mg qd 14/14	Vemurafenib progressors, PTPs, and PUPs	Cohort 4 will open to new patients only after both Cohorts 2 and 3 dose combinations are deemed safe and tolerable
5 (n=3-6)	960 mg bid/100 mg qd 14/14	Vemurafenib progressors, PTPs, and PUPs	
Cobimetinib monotherapy (up to 20)	60 mg qd 21/7	Vemurafenib IB progressors only	

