
Abbreviations: PTPs= patients previously treated for locally advanced/unresectable or metastatic melanoma but without prior exposure to any BRAF or MEK inhibitor therapy; PUPs = previously untreated patients with BRAF^{V600E} mutation-positive, locally advanced/unresectable or metastatic melanoma

*New cohorts not represented in Amendment C.

†New cohorts not represented in Amendment D.

Dose De-Escalation

The dose-escalation plan for vemurafenib and cobimetinib combination therapy may not be tolerable. In this case, a dose de-escalation plan may be adopted at the discretion of the study Sponsor.

If the Cohort 1 dose combination is not tolerated, dose de-escalation for either vemurafenib or cobimetinib will occur. Dose de-escalation will occur with simultaneous

enrollment into Cohort -1 (in which only vemurafenib is de-escalated to a lower dose level of 480 mg bid) and Cohort -2 (in which only cobimetinib is de-escalated to a lower dose level of 40 mg on a 14/14 schedule). If Cohort -1 or Cohort -2 dose combinations are not tolerated, there may be one further dose de-escalation to Cohort 3 (in which both vemurafenib and cobimetinib doses are decreased).

Table 6 Roadmap for Planned Dose–De-escalation Cohorts in the Setting of Cohort 1 Failure

Cohort	Vemurafenib	Cobimetinib (14/14 schedule)
-1	480 mg bid	60 mg qd
-2	720 mg bid	40 mg qd
-3	480 mg bid	40 mg qd

Table 6 outlines potential vemurafenib and cobimetinib dose combinations planned for Cohorts -1, -2, and -3 if needed. As described above, these potential cohorts would only be opened if dose de-escalation is needed because the Cohort 1 dose combination is not safe and tolerable.

If the Cohort 1A, 1B, 1C, or 1D dose combination is not tolerated, dose de-escalation for cobimetinib may occur at the Sponsor’s discretion. Table 7 outlines the vemurafenib and cobimetinib dose combination planned for Cohorts -1A, -1B, -1C, and -1D, if needed. These cohorts would only be opened if the dose combination tested in Cohort 1A, 1C, and 1D are not deemed safe and tolerable.

Table 7 Roadmap for Planned Dose De-Escalation Cohort in the Setting of Cohorts 1A, 1C, or 1D Failure

Cohort	Vemurafenib	Cobimetinib (21/7 schedule)	Cobimetinib (28/0 schedule)
-1A	720 mg bid	40 mg qd	NA
-1B	960 mg bid	40 mg qd	NA
-1C	720 mg bid	NA	40 mg qd
-1D	960 mg bid	NA	40 mg qd

NA= not applicable.

Cohort Assignment

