- The highest dose level(s) at which fewer than one-third of patients (e.g., 1 out of 6) experiences a DLT will be declared the MTD(s). If only 3 patients were initially evaluated at that dose level, an additional 3 patients will be enrolled to evaluate for DLTs at that dose level. It is possible that more than one MTD combination may be determined, e.g., if the dose combinations in Cohorts 2 and 3 are both deemed to be safe and tolerable and the dose combination in Cohort 4 is not; or if there are different MTDs for the combination of vemurafenib with cobimetinib dosed on a 14/14, 21/7, or continuous daily schedule. In these cases, more than one combination MTD dose and schedule may be expanded. A minimum of two expansion cohorts (n= 20 per cohort) will be enrolled (see below), one consisting of patients who have progressed on vemurafenib monotherapy immediately preceding enrollment in this trial and the other consisting of previously untreated patients with locally advanced/unresectable or metastatic melanoma or those previously treated but without prior exposure to any BRAF or MEK inhibitor therapy.
- If the combination MTD is exceeded in Cohort 1 (in which cobimetinib is given on a 14/14 schedule), further dose escalation will be discontinued, and instead, dose de-escalation with Cohort -1, -2 and Cohort -3 may occur (see [Table 6](#)). If the combination MTD is exceeded in Cohort 1A (in which cobimetinib is given on a 21/7 schedule), dose de-escalation with Cohort -1A may occur. If the combination MTD is exceeded in Cohort 1B, 1C, or 1D, dose de-escalation in Cohort -1B, -1C, or -1D, respectively, may occur (see [Table 7](#)).
- After dosing has been completed in each cohort, data pertaining to dose-escalation decisions will be reviewed by a committee composed of the following Sponsor representatives: Roche/Genentech Medical Monitor, statistician, Roche/Genentech safety officer with consultation from the PK scientist and Global Studies Leader. Investigator input will be provided by the principal investigators.

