Patients in the expansion stage (Stage 2) of the study will undergo the same tumor, safety, PD marker, biomarker, and PK assessments as those enrolled in the dose-escalation cohorts. Note: PK assessments upon disease progression, at the time of DLT, and at the time of dose reduction/treatment interruption due to adverse events were no longer required as of protocol amendment j.

If the frequency of Grade 3 or 4 toxicities or other unacceptable chronic toxicities in the cohort-expansion stage suggests that the MTD has been exceeded at that dose level, any remaining accrual at that dose level will be halted. Consideration will then be given to enrolling expansion cohorts at a lower dose combination level.

As noted above, it is possible that more than one MTD combination will be defined, consisting of different dose combinations and/or schedules of vemurafenib and cobimetinib that are deemed safe and tolerable. If this occurs, it is possible that more than two expansion cohorts will be enrolled to gather additional safety, PK, and PD data at these MTD combinations and schedules.

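### On the 14/14 schedule, the intrapatient escalation rule never states that the resulting vemurafenib/cobimetinib pair must already have been cleared

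*Combined protocol and SAP*

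**What the plan says.** Section 3.1.1 bars intrapatient escalation during the 28-day DLT window. After it, a patient without progression "may receive cobimetinib at the highest cohort dose level for which there are at least 4 weeks of safety data". Acceptable tolerability means no DLT among 3 evaluable patients, or at most one among 6. More than one level may be skipped. The worked example is that, once Cohort 2A clears, Cohort 1 and 2 patients may go to 100 mg; it gives no vemurafenib dose. Changes within one cobimetinib schedule are allowed "once the next higher dose level(s) is deemed to be acceptably safe and tolerable".

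The next paragraph covers vemurafenib in all these cases: "the daily dose of vemurafenib may remain the same (at 720 or 960 mg bid) or increase from 720 to 960 mg bid". One condition is attached to the rise, and it concerns the patient's own treatment just before entering this trial: "but only if the patient was tolerating 960 mg bid in a previous clinical study or postmarketing setting of vemurafenib monotherapy".

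For newly enrolled patients, the same section and Table 5 set the gates by dose combination: Cohort 4 needs Cohorts 2 and 3, and Cohort 5 follows Cohort 4.

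**The concern.** Newly enrolled patients reach 960/80 and 960/100 (vemurafenib mg bid / cobimetinib mg daily) only through gates that name the combination. Section 3.1.4 expects that Cohorts 2 and 3 may both be tolerable while Cohort 4 is not, so clearing 720/80 and 960/60 is not taken to clear 960/80.

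The intrapatient rule has no matching sentence. It sets cobimetinib by a cohort result and then lets vemurafenib rise on the patient's own monotherapy history. That history says nothing about 960 mg bid together with 80 or 100 mg of cobimetinib. At stake is whether some patients could receive, from Cycle 2 on, a pair that the trial has not yet shown to be tolerable. The combination is being given to humans for the first time here (Section 3.10).

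**Working it through.** **Inputs.** The 14/14 pairs and their gates, from Section 3.1.1 and Table 5:

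| Cohort | Pair | Opens after |
|---|---|---|
| 1 | 720/60 | start |
| 2 | 720/80 | Cohort 1 |
| 2A | 720/100 | Cohort 2 |
| 3 | 960/60 | Cohort 1 |
| 4 | 960/80 | Cohorts 2 and 3 |
| 5 | 960/100 | Cohort 4 |

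**Who could be affected.** Under Cohort Assignment in Section 3.1.1, patients previously on 960 mg bid may join the 720-mg cohorts after a dose reduction. Cohorts 1 and 2 can therefore include progressors who meet the condition for the vemurafenib rise.

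**Which uncleared pairs the text reaches.** The gates allow ten sets of cleared cohorts. Route A reads the cobimetinib step as a cleared pair (for example 720/100 from Cohort 2A) and then applies the vemurafenib sentence as written. Route B leaves vemurafenib at 960 and reads the cobimetinib level per drug, as for a Cohort 3 patient.

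| Cleared so far | Route A | Route B |
|---|---|---|
| 1, 2 | 960/80 | none |
| 1, 2, 2A | 960/80, 960/100 | none |
| 1, 2, 3 | 960/80 | 960/80 |
| 1, 2, 2A, 3 | 960/80, 960/100 | 960/80, 960/100 |
| 1, 2, 2A, 3, 4 | 960/100 | 960/100 |

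In the other five sets neither route reaches 960/80 or 960/100 uncleared. If Cohort 5 has cleared and 2A has not, the per-drug reading also admits 720/100. I do not count that, because the higher pair 960/100 is already cleared. So two of the six pairs are affected. Route A takes a Cohort 1 patient to 960/80 or 960/100 and a Cohort 2 patient to 960/100. Moving a Cohort 2 patient to 960/80 would be a vemurafenib-only rise, which the sentence may not cover.

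**Dose steps.**
- Cohort 1: cobimetinib 80/60 = 1.33 or 100/60 = 1.67, with vemurafenib 960/720 = 1.33.
- Cohort 2: cobimetinib 100/80 = 1.25, with vemurafenib 1.33.
- Cohort 3: cobimetinib 1.33 or 1.67, vemurafenib unchanged.

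Neither drug exceeds its single-agent MTD (960 mg bid; 100 mg on 14/14).

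**Timing.** Let T be the day Cohort 2 clears.
- 960/80 would be permitted from T. Cohort 4 opens no earlier than T and needs a 28-day window, so it clears no earlier than T + 28. The lead is at least 28 days.
- 960/100 would be permitted when Cohort 2A clears, at T + 28 at the earliest. Cohort 5 opens after Cohort 4 and clears no earlier than T + 56. With minimum windows the lead is 56 − 28 = 28 days. It shrinks or vanishes if 2A is slow.

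Increases start on Day 1 of a cycle, so actual exposure before clearance may be shorter than the lead.

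**Table 13.** All twelve entries reproduce. At a DLT rate of 0.20, the chance of enrolling three more is 3 × 0.2 × 0.8² = 0.384 (stated 0.38), and the chance of being judged tolerated is 0.8³ + 0.384 × 0.8³ = 0.709 (stated 0.71). These figures rest on Cycle 1 only, so later-cycle dosing does not enter them.

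**How the term is used.** *Dose level* means one drug in the starting-dose text (60 mg, "which is two dose levels below the single-agent MTD of 100 mg per day") and in de-escalation (Cohort -2, "in which only cobimetinib is de-escalated to a lower dose level of 40 mg on a 14/14 schedule"). It means the combination in the MTD rule of Section 3.1.4 ("The highest dose level(s) at which fewer than one-third of patients") and in Section 3.2 ("enrolling expansion cohorts at a lower dose combination level"). Usage elsewhere therefore does not settle it.

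**The case against.** The strongest reply is that the local wording points to the combination. The phrase is *cohort* dose level, a cohort is a vemurafenib/cobimetinib/schedule combination, and the criterion counts DLTs in a cohort. The sentence on the next higher level names neither drug, so it can govern a vemurafenib rise too. The vemurafenib sentence would then add a patient-level condition without removing the clearance condition. The worked example names only the two 720-mg cohorts below 2A and omits Cohort 3. All of this stands as support for a combination reading, under which there is no gap. It does not supply the missing statement: the example leaves the vemurafenib dose open, and the next paragraph then allows the rise.

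The second reply is that controls exist. Section 6 has the sponsor handle drug assignment. Section 3.1.4 gives clearance review to a sponsor committee and lets the sponsor halt or modify escalation. Multiple step-wise increases need Medical Monitor agreement. Escalation stops after cobimetinib-related Grade 3 or higher toxicity. Patients limited to 720 mg by tolerability are barred from 960-mg combinations, and Table 12 governs later toxicity. These lower the risk, and they count against inferring that a site could give an uncleared pair on its own reading. None says that the pair must be cleared, and Section 6 does not expressly mention later-cycle increases.

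Third, once Cohorts 2 and 3 clear, new patients receive 960/80 in Cohort 4 by design, so a Cohort 3 patient who has completed a cycle is not evidently at greater risk. That is fair for 960/80 but does not reach 960/100. Figure 4 is not shown here, so any limit drawn in it cannot be checked.

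**Conclusion.** The point holds as a minor patient-safety improvement, with medium confidence. On a literal reading, the vemurafenib permission lets a Cohort 1 or 2 progressor reach a pair still awaiting clearance. The Cohort 3 route needs the further assumption that the cobimetinib level is read per drug. The number of patients affected cannot be derived. At Version L, with a clinical study report already written (Section 18), the practical effect is probably small.

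A reader might infer more, and the documents do not support it:
- That the protocol intends uncleared pairs to be given. The combination reading is reasonable.
- That the DLT counts or the MTD are compromised. Both rest on Cycle 1, when intrapatient escalation is barred.
- That 960/80 would remain available after Cohort 4 failed. Section 3.1.4 would then class that combination as intolerable, which would probably stop it even though the intrapatient rule is silent.

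**What to change.** After the vemurafenib sentence in Section 3.1.1, add: *An intrapatient increase of either drug is allowed only if the resulting vemurafenib/cobimetinib/schedule combination has itself met the tolerability criterion above (0 DLTs in 3 or at most 1 in 6 evaluable patients, with at least 4 weeks of safety data).* Beside the existing example, add one at 960 mg: *a Cohort 3 patient may go to 80 mg only after Cohort 4 has cleared.*

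With this rule, no uncleared pair is permitted in any of the ten sets of cleared cohorts. It needs two sentences and no extra patients or procedures. The downside is that some patients wait longer for an increase, or stay at the lower dose if Cohort 4 or 5 never clears.

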3.1.2 Option to Receive Single-Agent Cobimetinib

Enrollment in this cohort is limited to 20 patients and will require the approval of the Medical Monitor. See Section 3.1.1 for details on the eligible patient population.

Dosing for Single-Agent Cobimetinib

For patients receiving single-agent cobimetinib, all cycles will be 28 days. cobimetinib dose will be 60 mg qd on Days 1–21, followed by 7 days off on Days 22–28 (Figure 7).

Figure 7: Dosing Schema for Patients Receiving Single-Agent Cobimetinib

3.1.3 Dose-Limiting Toxicity Assessment Window

For all patients enrolled in the vemurafenib and cobimetinib combination cohorts, DLTs will be assessed during a DLT assessment window of 28 days in Cycle 1. The 28-day DLT window will not apply for patients treated with single-agent cobimetinib.

Dose reductions are not allowed during the DLT window for a patient to count in dose-escalation decisions.

Patients who discontinue study treatment or miss 3 or more total days of either vemurafenib or cobimetinib prior to completing the DLT assessment window for any reason other than DLT will be replaced.

3.1.4 Rules for Dose-Escalation and Potential Dose De-Escalation; Changes in Dose Scheduling following Dose-Limiting Toxicity

Dose escalation will occur in accordance with the rules listed below. Intra-cohort dose escalation is not allowed.

- A minimum of 3 patients will be initially enrolled per cohort
- If 1 of the first 3 patients enrolled in a given cohort experiences a DLT, at least 3 additional patients will be enrolled in that cohort.
- If fewer than one-third of evaluable patients in a given cohort experiences a DLT (e.g., DLTs in fewer than 1 of 3 or 2 of 6 patients), escalation will proceed to the next higher dose cohort.
- If a DLT is observed in one-third or more of patients (e.g., 2 or more of up to 6 patients), the dose combination at which this occurs will be considered intolerable, and the MTD will have been exceeded.

- The highest dose level(s) at which fewer than one-third of patients (e.g., 1 out of 6) experiences a DLT will be declared the MTD(s). If only 3 patients were initially evaluated at that dose level, an additional 3 patients will be enrolled to evaluate for DLTs at that dose level. It is possible that more than one MTD combination may be determined, e.g., if the dose combinations in Cohorts 2 and 3 are both deemed to be safe and tolerable and the dose combination in Cohort 4 is not; or if there are different MTDs for the combination of vemurafenib with cobimetinib dosed on a 14/14, 21/7, or continuous daily schedule. In these cases, more than one combination MTD dose and schedule may be expanded. A minimum of two expansion cohorts (n= 20 per cohort) will be enrolled (see below), one consisting of patients who have progressed on vemurafenib monotherapy immediately preceding enrollment in this trial and the other consisting of previously untreated patients with locally advanced/unresectable or metastatic melanoma or those previously treated but without prior exposure to any BRAF or MEK inhibitor therapy.
- If the combination MTD is exceeded in Cohort 1 (in which cobimetinib is given on a 14/14 schedule), further dose escalation will be discontinued, and instead, dose de-escalation with Cohort -1, -2 and Cohort -3 may occur (see [Table 6](#)). If the combination MTD is exceeded in Cohort 1A (in which cobimetinib is given on a 21/7 schedule), dose de-escalation with Cohort -1A may occur. If the combination MTD is exceeded in Cohort 1B, 1C, or 1D, dose de-escalation in Cohort -1B, -1C, or -1D, respectively, may occur (see [Table 7](#)).
- After dosing has been completed in each cohort, data pertaining to dose-escalation decisions will be reviewed by a committee composed of the following Sponsor representatives: Roche/Genentech Medical Monitor, statistician, Roche/Genentech safety officer with consultation from the PK scientist and Global Studies Leader. Investigator input will be provided by the principal investigators.

This committee will review available relevant data on demographics, adverse events, laboratory assessments, 12-lead ECGs, and dose administration logs, as well as PK data. On the basis of a review of these data and in consultation with the participating investigators, a determination will be made as to whether dose escalation should continue, and if so, at what level and schedule. The selection of a recommended Phase II dose and schedule will depend upon results of the safety, activity, and PK evaluations from all patients treated in both the dose-escalation and cohort-expansion stages.

The overall vemurafenib and cobimetinib dose-escalation/de-escalation plan is depicted in [Figure 4](#), [Figure 5](#), [Table 5](#), [Table 6](#), and [Table 7](#).

On the basis of a review of available safety and PK data during this and other studies with both agents, dose-escalation may be halted or modified by the Sponsor, in consultation with investigators as deemed appropriate for safety concerns.

